Effect of Low-pressure Pneumoperitoneum on Pain and Inflammation Post Laparoscopic Cholecystectomy: A Randomized, Double-blinded, Controlled, Clinical Trial.

ClinicalTrials.gov Identifier: **not yet assigned**

Date protocol accepted by IRB at the University of Jordan: **15th January 2020**

Study Summary:

In the era of laparoscopic abdominal surgeries, pneumoperitoneum pressure is set to a point of 12-15 mmHg. The new generation of surgeon has been questioning if we could do laparoscopic surgeries with no compromise at a lower pneumoperitoneum pressure in the aim of improving the quality of patients' lives postoperatively and efficacy of health care system. In reviewing the literature, such intervention has showed benefit in terms of decreasing postoperative pain (1) and rise of inflammatory markers (2). This study is designed as a randomized double- blinded controlled clinical trial to challenge such hypothesis. The study shall be conducted on patients at The University of Jordan hospital booked electively for laparoscopic cholecystectomy then randomized into two groups operated at either standard or low pneumoperitoneum pressure then assessed post operatively for pain and rise of inflammatory markers.

Research design:

It is a clinical trial, designed to look for a statistical difference in pain and rise of inflammatory markers post operatively between interventional group which is operated at a low-pressure pneumoperitoneum of 8-10 mmHg compared to the standard of care of pneumoperitoneum set at a pressure of 12-14 mmHg.

further to increase validity of results and strengthen the study design, the study participants are randomized, the groups are masked, and the data is blinded to investigators, analyst, and participants.

Research subjects:

All patients admitted to surgery ward through clinic with the diagnosis of multiple gallbladder stones undergoing laparoscopic cholecystectomy are to be considered for enrollment in this study.

Inclusion criteria:

- Elective admission for laparoscopic cholecystectomy
- Minimum age of 12 years
- American Society of Anesthesiologists (ASA) score 1 or 2

Exclusion criteria:

- Current or previous diagnosis of acute cholecystitis confirmed by ultrasound.
- previous GI surgeries, except bariatric and anti-reflux surgeries
- Currently on immunosuppressant agents
- Pregnancy
- Breastfeeding
- Currently diagnosed with drug addiction
- American Society of Anesthesiologists (ASA) score 3, 4, 5, or emergency surgery

Allocation to groups:

participants are to be given numbers in study and be labeled with it. A preset computer-generated list is to be used to divide patients between two study arms into either of masked groups. Allocation to groups is random according to the computer-generated randomized list.

Masking (blinding) method:

The two study arms are to be color coded. The codes are to be used for randomization, data entry and analysis. None of the participants, investigators and analyst are to be informed of color code reference. the principal investigator, operating surgeon and circulating nurse during operation are to be informed of the color code meaning. After closure of the study, the color codes can be disclosed to the public.

Criteria to discontinuation:

Any participant withdrawing consent during any time of the study.

Patients found to have intra operative adhesions and evidence of previous inflammation are not to be discontinued from the study.

Sample size:

A convenient sample of 100 participants is decided, divided into 50 for each study group.

Intervention:

Interventional group is to be operated at low-pressure pneumoperitoneum which is set at 8-10. Control group is to be operated at standard-pressure pneumoperitoneum which is set at 12-14. The pressure set point is to be determined at the beginning of surgery, any change to pressure after initial insufflation is not to change the participants study arm grouping.

Observations:

Pre-operative demographics are to be collected for each patient, including patient name, medical record number (MRM), age, gender, weight, height, ASA score, medical history, surgical history, current medications, marital status, smoking status, operation date.

During operation, the following are to be observed and recorded: time of surgery start, time of surgery end, total time of insufflation, method of insufflation (open, closed), operator level of experience, intraoperative findings (adhesions, inflammation, perforation, bile leak), difficulty of surgery subjectively assessed by operator (easy, moderate, difficult), estimated blood loss, change of pneumoperitoneum pressure set point, intraoperative mortality, intraoperative complications.

Post-operative during hospital-stay the following are to be collected: pain score out of 10 according to patient perception recorded at 6hr, 12hr and 24hr post-op, hospital stay length in days, total analgesia given post-op (number of dosage and type).

Post-operative after hospital discharge the following are to be collected: pain score out of 10 according to patient perception recorded on 7th day post-op and to be collected via phone call, post-operative complications up to day 30 (readmission, CBD stone, pancreatitis, cholangitis, ..etc.), and histopathology result.

The following inflammatory markers are to be investigated: white blood cell count, platelet count, erythrocyte sedimentation rate, C reactive protein level, albumin level, free serum cortisol level, interleukin-6 level, interleukin-17 level, interleukin-1 beta level, tumor necrosis factor alpha level.

Flow of study work:

After ensuring patients eligibility for study and obtaining informed consent, they are to be allocated to one of study arms randomly. Observations are to be taken and entered to on-line excel. After discharge patients are to be followed on day 7 post-op to collect pain score via phone call, complications are to be followed up to day 30 post-op from electronic records.

Regarding inflammatory markers, the tests are to be performed at Jordan University Hospital laboratories, the blood samples are to be collected safely by study assistants and delivered to the lab labeled with patient name, MRM, date, and time of collection. The runoff tests are done as standardizes by hospital laboratory policies.

Specifications to operation:

Patients enrolled in the study are to undergo laparoscopic cholecystectomy as per the following protocol:

- Regarding general anesthesia, the use of dexamethasone during induction is to be avoided
- Regarding creation of pneumoperitoneum, the choice is given to operating surgeon to choose either open, closed, or optical technique
- Regarding number and site of trocars, the choice is given to operating surgeon to perform as per trained
- Cholecystectomy is to be performed as standardized, after establishment of critical view of safety, the operating surgeon is to carry on steps to establish hemostasis, clipping of cystic duct, and dissection of gallbladder from its liver bed
- Retrieval of specimen is to be done through umbilical port
- The use of endoclose device for closure of fascia is to be avoided
- The infiltration of local anesthesia at site of trocars is to be avoided
- Regarding skin closure, the choice is given to operating surgeon to perform as per trained

Data management and analysis:

The principal investigator is to ensure adherence to protocol and data validity. To ensure this, data will be reviewed each end of month, and a progress summary is to be written and provided to study regulatory every six months.

Analysis is to be conducted using SPSS version 1.0.0.1406. analysis plan is attached in separate file.

Ethical considerations:

No data to be collected without obtaining patient informed consent, the signed paper is to be kept for a minimum of two years

Funding:

The study is funded by a grant through the University of Jordan scientific research deanship.

References:

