Analysis was conducted using SPSS version 1.0.0.1406. Gender, smoking status, ASA score, and difficulty of surgery were analyzed using Chi-square cross table. Mean duration of total operative time, insufflation time, and mean hospital-stay were analyzed using Student's 2-tailed t-test. The mean intensity of pain was analyzed using Mann-Whitney U test. Inflammatory markers (WBC, Plt, ESR, CRP, Albumin, Cortisol, IL-6, IL-17, TNF- α , IL-1 β) levels were analyzed using Welch's t-test. Subgroup analysis for the inflammatory markers was done to eliminate the effect of dexamethasone given by anesthesia team at the time of anesthesia induction, analysis was done using Welch's t-test. All test set *p*-value was set at 0.05 to consider results significant.

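### One colour code labels the randomisation list and is disclosed to the principal investigator, surgeon and nurse during enrolment, and no described safeguard keeps upcoming entries from them

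*Protocol*

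**What the plan says.** Five statements in the protocol bear on this.

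- Allocation to groups: "A preset computer-generated list is to be used to divide patients between two study arms into either of masked groups".
- Masking (blinding) method, on the code itself: "The two study arms are to be color coded", and "The codes are to be used for randomization, data entry and analysis".
- Masking (blinding) method, on who is kept unaware: "None of the participants, investigators and analyst are to be informed of color code reference".
- Masking (blinding) method, on who is told: "the principal investigator, operating surgeon and circulating nurse during operation are to be informed of the color code meaning".
- Flow of study work, on the order of events: "After ensuring patients eligibility for study and obtaining informed consent, they are to be allocated to one of study arms randomly".

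Neither document says who generates or holds the list, whether upcoming entries are hidden, how an assignment is released, or who screens patients and judges eligibility. The SAP lists unadjusted chi-square, t, Mann-Whitney and Welch tests.

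**The concern.** The surgeon and the theatre team need to know the pressure for the patient on the table. The protocol gives them more than that: the meaning of a label shared by every patient in the arm. No recoding by patient or by operation is described, so one disclosure during the trial is enough to decode the colours from then on. The colours are the only protection of the list that the documents describe, and for these three roles that protection is removed.

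What is at stake is selection at entry. If someone who can decode the next entry also influences who is enrolled, an elective candidate can be deferred or graded out of the trial. ASA 2 versus ASA 3 is one criterion that leaves room for judgement. The arms could then differ before surgery, and the SAP's unadjusted tests would not correct for it. Masking participants and the analyst does not guard against this.

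**Working it through.** **What the text implies, step by step**

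1. There are two arms and one colour per arm, so the key has two entries.
2. The same colours are used for randomisation and in the data file, so the preset list can be read with that key.
3. The key is given to the principal investigator, operating surgeon and circulating nurse in connection with operations, and so before the study closes.
4. A key-holder who sees the next entry therefore knows the next arm. Obtaining eligibility and consent before allocation does not prevent this if the entry is already visible.
5. A key-holder who does not see the list does not know the next arm. The documents do not say which situation applies.

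**How far the key leads if upcoming entries are hidden**

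The plan states no figure on this point beyond 50 + 50 = 100. Suppose a key-holder knows all past allocations and always guesses the arm with more places left. In a balanced block of 2m, the expected number of correct guesses is m + 2^(2m-1)/C(2m, m) - 1/2. The documents give no block scheme, so block sizes are assumptions.

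| List | Correct guesses |
|---|---|
| One unblocked list of 100 (m = 50) | 55.78 of 100 = 55.8% |
| Blocks of 8 | 5.33 of 8 = 66.6% |
| Blocks of 6 | 4.10 of 6 = 68.3% |
| Blocks of 4 | 2 + 8/6 - 0.5 = 2.83 of 4 = 70.8% |
| Blocks of 2 | 1.5 of 2 = 75.0% |

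Chance is 50%. If the next entry is visible, the figure is 100%.

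**What steering would do to the test**

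From the documents: 50 per arm and a 0.05 significance level (SAP). All other inputs are assumptions:

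- share q of candidates expected to be difficult: 0.2 to 0.3;
- shift d in pain or log-marker level for these patients: 0.5 to 1.0 SD (the SD among patients of the same difficulty);
- the next arm is always known;
- a fraction v of difficult candidates due for low pressure is deferred and does not return.

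Formulas:

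- difficult share in the low-pressure arm: s = q(1 - v)/(1 - qv);
- bias favouring low pressure: (q - s) × d;
- outcome SD: √(1 + q(1 - q)d²);
- noncentrality: bias/SD × √(50/2), in a two-sided t-test on 98 degrees of freedom.

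Example with q = 0.3, d = 1, v = 0.5: s = 0.15/0.85 = 0.1765; bias = 0.1235; SD = √1.21 = 1.10; noncentrality = 0.1235/1.10 × 5 = 0.56; false-positive rate 8.6%.

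| Deferred (v) | Bias (SD) | False-positive rate |
|---|---|---|
| 0 | 0 | 5.0% |
| 0.10 | 0.008-0.022 | 5.0-5.1% |
| 0.25 | 0.021-0.057 | 5.1-5.8% |
| 0.50 | 0.044-0.124 | 5.5-8.6% |
| 1.00 | 0.10-0.30 | 7.7-27.2% |

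The last row is a bound. At q = 0.3 it needs 50/0.7 - 50 = 21 candidates turned away to fill the low-pressure arm.

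If entries are hidden and only the 55.8% guess is acted on, every time, then 55.8% of difficult candidates due for low pressure are deferred and 44.2% of those due for standard pressure. At q = 0.3 and d = 1 the difficult shares are 0.3 × 0.442/(1 - 0.3 × 0.558) = 0.159 and 0.3 × 0.558/(1 - 0.3 × 0.442) = 0.193. The bias is 0.034 SD and the false-positive rate about 5.3%.

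**The case against.** A reader might infer that a surgeon told the code once knows every later assignment and can choose who enters. The documents do not support that. Knowing a later assignment needs sight of the upcoming colours as well as the key, and nothing says that any key-holder sees the list. Nor do the documents say that the operating surgeon, or anyone else with the key, screens patients. Investigators are stated not to be told the code, so for a masked recruiter the colours do hide the arm. Eligibility and consent come before allocation. A past diagnosis of acute cholecystitis excludes only if confirmed by ultrasound, so it is a weak example of a discretionary criterion.

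The bias figures are also open to challenge. Prevalence, shift and deferral rate are all assumed, perfect foreknowledge is built in, and deferred patients are treated as lost although they might return. No motive for one-way deferral is documented, and a change of pressure during surgery does not move a patient between arms. The SAP compares ASA score and surgical difficulty by arm, which could reveal some imbalance but would not correct it.

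All of this stands, and it limits the point to an exposure that the plan leaves open. It does not remove the exposure, because the protocol itself puts the shared key in the hands of three roles and describes no other concealment.

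**Conclusion.** The point holds as a weakness in allocation concealment that should be corrected. It is not evidence that anyone foresaw or steered assignments. What rests on the text is that one colour per arm serves randomisation, data entry and analysis, and that its meaning is disclosed during the trial. That the colours stay the same throughout is a fair inference, since no recoding is described, but it is not stated outright.

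The size of any bias cannot be derived from the documents. Under the stated assumptions, modest steering (10-25%) leaves the test close to its nominal level, and deferral of half the relevant cases raises the false-positive rate to at most 8.6%. Values near 27% need complete one-way deferral and should not be read as an expectation.

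Separately, the masking paragraph contradicts itself. Investigators are not to be told the code, yet the principal investigator is, and that same role is responsible for data validity, with data reviewed every month (Data management and analysis). These statements must be reconciled.

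**What to change.** 1. Record and date eligibility, ASA score and consent before the assignment is released. The protocol already has this order; the dated record and the hidden assignment are what is new.
2. Replace the colour list with sequentially numbered, opaque, sealed envelopes. Each states the arm for one patient number only and is opened in theatre just before insufflation. Whoever generates the list prepares them, and that person neither enrols nor operates.
3. Keep a separate colour label for data entry and analysis. Do not tell its meaning to anyone who enrols, operates, reviews data or analyses. People who were in theatre should not see the colour column beside patient numbers, because they could work out the key by matching.
4. State in the protocol who generates and holds the list, and resolve the conflict over whether the principal investigator is told the code.

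The cost is about 100 envelopes, two reworded paragraphs, and some time from an existing colleague outside enrolment and surgery. The documents describe no such role, so one must be named. No patients or procedures are added, and the surgeon still learns the setting for each operation.

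One limit remains: the surgeon will still know past arms, so small fixed blocks would leave the next arm partly guessable (70.8% for blocks of 4). If blocks are used, their sizes should not be disclosed to those who enrol or operate.

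### The principal investigator is told the meaning of the arm colours that label the data and also answers for data validity, so the stated masking of investigators does not hold for that role

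*Protocol*

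**What the plan says.** The statements are all in the protocol; the SAP does not mention masking.

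- Research design: "the data is blinded to investigators, analyst, and participants".
- Masking (blinding) method, on the code: "The two study arms are to be color coded", and "The codes are to be used for randomization, data entry and analysis".
- Masking (blinding) method, on who is kept unaware: "None of the participants, investigators and analyst are to be informed of color code reference".
- The sentence directly after that: "the principal investigator, operating surgeon and circulating nurse during operation are to be informed of the color code meaning".
- Flow of study work, on where data are held: "Observations are to be taken and entered to on-line excel".
- Data management and analysis, on who answers for the data: "The principal investigator is to ensure adherence to protocol and data validity. To ensure this, data will be reviewed each end of month". The review is in the passive voice, so the person who performs it is not named.
- Allocation to groups: "participants are to be given numbers in study and be labeled with it". An identifier that does not reveal the arm therefore already exists.

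**The concern.** Taken together, these statements give one person both the key to the arms and the responsibility for whether recorded values are valid. Two things are at stake.

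The first follows from the text alone. A report that repeated the Research design sentence without qualification would be inaccurate for the principal investigator.

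The second is a risk. Neither document has a rule for correcting, voiding or excluding a recorded value, or asks for a log of changes, so any such decision would rest on judgement. The Study Summary shows which result is expected: less pain and a smaller rise in markers at low pressure. Masking is the usual way to keep such judgements even between arms, and judging whether a pain score or laboratory value is valid does not require knowing the arm.

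**Working it through.** The plan gives no figure on this point, so the main check is a comparison of statements.

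**Step 1. Does the principal investigator know the code?** Yes. The masking section names that role among the three who are told. The sentence before it and the Research design section both say investigators are not told, and neither makes an exception.

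**Step 2. How much does the code reveal?** There are two arms with one fixed colour each. Learning the meaning once decodes 50 + 50 = 100 of 100 records (Sample size section). The phrase about the operation may limit when the code is disclosed, but the knowledge remains for every later monthly review.

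**Step 3. Is that code in the data?** Yes. The masking section uses it for data entry and analysis.

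**Step 4. Does the principal investigator have a duty towards those data?** Yes, for validity as well as adherence, although the text does not say who carries out the review.

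So the person who answers for validity can read the arm of every record. Nothing in these steps reaches the other investigators, the analyst or the participants.

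**Illustration of size (assumed inputs).** The documents give no outcome distributions and describe no voiding of values. The assumptions are: 50 per arm, no true effect, two-sided 0.05, and the SAP's tests (Mann-Whitney for pain, Welch's t-test for markers). Pain is a rounded normal score with mean 4 and SD 2, cut to 0-10. Markers are either normal or log-normal with log-SD 1. The entries are simulated false-positive rates.

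| Values voided | Pain | Normal marker | Log-normal marker |
|---|---|---|---|
| None | 5.0% | 5.0% | 4.2% |
| Highest 1, low-pressure arm only | 5.6% | 6.2% | 7.0% |
| Highest 2, low-pressure arm only | 6.9% | 8.1% | 11.9% |
| Highest 3, low-pressure arm only | 8.7% | 10.7% | 18.3% |
| 3 at random from the ten highest, low-pressure arm only | not run | 7.4% | 6.7% |
| Highest 2 low-pressure, highest 1 standard | about 6% | 6.9% | 9.6% |
| 3 from one arm regardless of size | not run | no inflation | no inflation |
| Highest 3 of all 100, arm unknown | 4.9% | not run | 4.8% |

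The rows that void the highest one, two or three values in the low-pressure arm alone are close to a worst case. The log-normal column starts from 4.2%, not 5%, because Welch's test is slightly conservative there. A repeat simulation agreed with the table to within simulation error.

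**The case against.** The strongest reply is that the masking section states a general rule and then at once names three exceptions, so the principal investigator's knowledge is declared. On that reading the other investigators stay masked. This stands as a limit on scope. A reader might infer that the data are unmasked to investigators as a group, and the documents do not support that. The Research design sentence is still inaccurate for the principal investigator, because it allows no exception.

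A second reply is that the monthly review also serves protocol adherence. Whether the set point matched the allocated arm (8-10 or 12-14) cannot be checked without the arm, so knowing the code has some purpose. This is correct, but it justifies a separate adherence check and not arm labels in the validity review.

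A third reply is that no route to bias is described. Pain is the patient's own rating. Markers are run under hospital laboratory policy on samples labelled with name, record number, date and time, with no colour listed. Withdrawal of consent is the only discontinuation criterion. No section says the principal investigator reviews the file personally, edits or voids values, or collects scores. This also stands. A reader might infer that outcomes were tilted, or that the error rate is 11% or 18%. The documents support neither: those figures require removing exactly the three highest values from one arm, which is nearer to manipulation than to uneven judgement. The missing rules for correcting values are a data-management gap and not evidence that discretion was used.

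Finally, the surgeon and circulating nurse must know the pressure. That is unavoidable and is not criticised here. They need the set point for the patient in front of them, not the key to the data file.

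**Conclusion.** The point holds for one role. The principal investigator is told a fixed two-colour code that labels the data and also answers for data validity, so the plan's statement that data are masked to investigators is not accurate for that person. Participants, the analyst and the other investigators may be masked as written.

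It is a masking gap and a wording error; no bias is shown. The certain part is that one disclosure decodes 100 of 100 records. Any effect on the results depends on events the documents do not describe: it is zero if no value is changed, and about 7% in place of a nominal 5% if three of the ten highest marker values in the low-pressure arm are voided. Larger figures are worst-case illustrations. Severity: minor.

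**What to change.** **If data are still being collected:**

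- Enter data under the existing study number and add the colour only after data lock.
- Give theatre staff the set point for each patient, for example in a numbered sealed envelope, and not the colour key. Do not tell the principal investigator the key.
- Run the monthly validity review on a file without colour or set-point fields, and log every changed value with its previous entry and the reason.
- Have set-point adherence checked separately by someone who already knows the pressure, such as theatre staff.

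**If data are already collected**, as the SAP's past tense suggests:

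- Correct the Research design sentence to say: blinded to participants, the analyst and investigators other than the principal investigator and operating surgeon; the principal investigator, operating surgeon and circulating nurse knew the code.
- Report by arm any values known to have been changed or excluded, if the history of the entry sheet allows it. The documents mention no audit trail, so this may not be possible.

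**Cost.** No extra patients and no change to surgery or ward care. It takes up to 100 envelopes, columns withheld from the review file until lock, and a change log. The small downside is that the adherence check is split from the validity review. An outside key holder or a second reviewer would be extra staff and is not essential.

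### Operative and insufflation time are compared without adjustment although prognostic values are recorded: a minor loss of precision, with operator level a safe covariate only if the operator is fixed before allocation

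*Protocol*

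**What the plan says.** The Observations section of the protocol lists weight and height among the pre-operative data. It then gives a second list, introduced by "During operation, the following are to be observed and recorded", which holds surgery start and end, total insufflation time and "operator level of experience". The experience categories are not defined.

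On assignment, the protocol says "Allocation to groups is random according to the computer-generated randomized list". It names no stratum, block or minimisation factor. The sample size is given as "A convenient sample of 100 participants is decided, divided into 50 for each study group", with no power, effect size or SD.

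The SAP states: "Mean duration of total operative time, insufflation time, and mean hospital-stay were analyzed using Student's 2-tailed t-test". It names no covariate for any outcome. Operator level does not appear in it at all, not even among the categorical comparisons: "Gender, smoking status, ASA score, and difficulty of surgery were analyzed using Chi-square cross table".

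**The concern.** Operative time plausibly depends on who operates and on the patient's build. Under Specifications to operation, the protocol leaves access technique, trocar placement and skin closure to the operating surgeon, so some variation between operators is to be expected in the measured times. The plan collects values that could absorb part of this variation and then does not use them.

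The Study Summary asks whether lower pressure can be used without compromise. The two times bear on that question, and they are more objective than the difficulty rating, which comes from a surgeon who knows the arm. A non-significant difference in time could be read as showing no cost, so the width of the interval matters. With a convenience sample of 100 and no stated power, precision available from data in hand is worth having.

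**Working it through.** **Inputs from the documents.** 50 per arm (protocol, Sample size); unadjusted two-sided t-test at 0.05 (SAP).

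**Assumed inputs.** The documents give no SD, no operator mix and no association between any covariate and time. The true difference is set at 0.5 SD. R², the share of within-arm variance explained by the covariates, is varied from 0 to 0.4.

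**The plan's own figure.** The 100 has no derivation, so there is nothing to reproduce. For reference, the normal approximation gives a detectable difference at 80% power of (1.960 + 0.842) × √(2/50) = 0.56 SD.

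**Step 1: precision and power.** In SD units, the unadjusted standard error is √(2/50) = 0.20. Adjustment reduces it to 0.20 × √(1 − R²). The non-centrality is 0.5 divided by that standard error, and power comes from the non-central t with 98 degrees of freedom (using 95 to 97 instead changes power by less than 0.1 point). The equivalent size is 50/(1 − R²) per arm, and the 95% CI half-width is 1.984 × SE.

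| R² | SE (SD) | Non-centrality | Power | Equivalent n per arm | CI half-width (SD) |
|---|---|---|---|---|---|
| 0 | 0.200 | 2.50 | 69.7% | 50 | 0.40 |
| 0.05 | 0.195 | 2.56 | 71.9% | 52.6 | 0.39 |
| 0.1 | 0.190 | 2.64 | 74.2% | 55.6 | 0.38 |
| 0.2 | 0.179 | 2.80 | 79.0% | 62.5 | 0.36 |
| 0.4 | 0.155 | 3.23 | 89.2% | 83.3 | 0.31 |

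**Step 2: validity and a check by simulation.** With 20,000 runs per setting and a binary covariate at 50%, the type I error of the unadjusted t-test was 4.9% to 5.0% for R² of 0 to 0.4. For a true difference of 0.56 SD, power was 79.5% unadjusted against 87.1% adjusted at R² = 0.2, and 79.1% against 78.8% at R² = 0.

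**Step 3: chance imbalance.** Suppose two operator levels with a share p senior. The exact difference of two Binomial(50, p) counts puts the arms 10 points or more apart in 32.6% of trials (p = 0.3) to 36.8% (p = 0.5), and 20 points or more apart in 3.8% to 5.7%. If the levels explain R² of the variance, their gap is √(R²/(p(1 − p))) SD. A 10-point imbalance then shifts the estimate by 0.1 times that gap: 0.06 to 0.10 SD for R² of 0.1 to 0.2, against a standard error of 0.20 SD.

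This is not an additional loss. The variance due to imbalance is gap² × 2p(1 − p)/50 = R² × 0.04. The residual part is (1 − R²) × 0.04. They sum to 0.04, the square of the 0.20 that the unadjusted test already uses.

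**Step 4: cost if the covariates explain nothing.** Two extra parameters raise the standard error by about √(97/95) = 1.010, or 1%.

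**Step 5: is operator level a baseline value?** Three statements in the protocol have to be read together. Flow of study work places allocation after consent and before observations are taken. Observations has operator level recorded during surgery. The Masking section has the principal investigator and operating surgeon informed of the code's meaning. Nowhere is the operator said to be fixed before allocation. The documents therefore do not establish that operator level is unaffected by arm. Weight and height are pre-operative and do not raise this problem.

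**The case against.** The strongest case against is that nothing here is an error. An unadjusted t-test in a randomised trial is legitimate and holds its level. The protocol's Research design section names pain and inflammatory markers as the objectives, and the two times are not among them. The size of the gain rests wholly on an assumed R²: it is about 2 power points at 0.05 and nil at 0, and nothing in the documents supports 0.4 in particular. All of this stands, and it is why the point is minor.

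A further objection is that adjusting for operator level has a price. If the operator is chosen, or a senior takes over, in response to the arm, operator level is a post-randomisation variable and conditioning on it could bias a comparison that is now unbiased. This also stands. It limits what may enter the main model, but it does not count against adjusting for BMI.

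Finally, the SAP is written in the past tense and mentions dexamethasone as already given. If the operations are complete, the condition on operator assignment can no longer be put in place, and only the fallback in the fix remains.

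A reader might infer that imbalance in operator level biases the time comparison or undermines its p-value. The documents do not support that for chance imbalance: the unadjusted standard error already allows for it, as step 3 shows.

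**Conclusion.** The point holds as a minor one about precision. Two secondary outcomes are analysed without covariates that the protocol already collects. Over R² of 0 to 0.4 the gain for a 0.5 SD difference runs from nothing to about 20 power points (69.7% to 89.2%), and the documents do not allow the range to be narrowed. The absence of a stratum is inferred from silence, since the protocol describes a list and names no factor.

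It would be tempting to conclude that operator level must be in the primary model because it is recorded anyway. That goes too far, because its baseline status is not secured. Nor does the point reach pain or the inflammatory markers, for which no such loss has been calculated here.

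**What to change.** - In the SAP, analyse operative time and insufflation time each with a linear model on arm plus pre-operative BMI (from the recorded weight and height), with robust standard errors. Report the adjusted difference with its 95% CI, and keep the unadjusted comparison as a sensitivity analysis.
- Define the operator-experience categories. Add operator level as a factor in the main model only if the operator is assigned and recorded before allocation.
- If that cannot be assured, tabulate operator level by arm and present the operator-adjusted model as supportive only.
- If the data are already unblinded, label the adjusted analysis post hoc.

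The cost is SAP wording and one model per outcome, with no new data field. A few degrees of freedom are spent, about 1% on the standard error if the covariates explain nothing. The one procedural demand is fixing the operator before allocation, and it applies only if operator level is to enter the main model.
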